8.3 Stratification Factors/ Randomization

Stratification will be based on the length of chemotherapy cycles, between 14-day (i.e. Ewing sarcoma patients receiving interval compressed chemotherapy) and 21-day cycles (most others). Site will not be a stratification factor. Subjects will be randomized with equal allocation to each arm using a stratified block randomization scheme with varying block sizes (of size 2 - 4).

8.4 Data Analyses Plans

Graphical and repeated measure models will be used to describe the complete pattern of ANC over all four cycles. Between-group (Cycles 1 & 2) and crossover differences (Cycles 1 - 4) form the structure for treatment comparisons. Repeated measure models

will be used to assess differences in raw ANC, daily ANC, days with fever, duration of hospitalization, and duration of antimicrobial use for subjects admitted with febrile neutropenia. The Cochran–Mantel–Haenszel test statistics will be used in the analysis of stratified categorical data such as neutropenia grades (severe: ≤ 100 cells/ μl ; moderate: ≤ 500 cells/ μl ; mild: ≤ 1000 cells/ μl) and filgrastim (G-CSF) usage. For duration and severity of mucositis and peripheral motor neuropathy, detailed physical examinations will be documented at each weekly physical exam. Grading (grade 1 - 5) will be performed according to the [CTCAE](#) guidelines, version 4.0. The Cochran–Mantel–Haenszel test will be used to compare grade and repeated measure models for duration of mucositis between cycles containing genistein versus placebo.

Number of subjects who experience hearing impairment and tinnitus will be summarized by treatment for each cycle. The number of required blood product transfusions, both packed red blood cells and platelets, will be documented and compared during genistein and placebo cycles using repeated measure models. Reporting will be in the form of total ml/kg body weight infused of red blood cells and platelets. Criteria for transfusion are listed in [Section 4.8.2](#).

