3.1 Inclusion Criteria

- [1] Newly diagnosed solid tumor or lymphoma with histological verification
- [2] Age 1 - 21 years at time of diagnosis
- [3] Karnofsky/Lanksy performance score of ≥ 50
- [4] Able to tolerate enteral medication administration
- [5] Planned chemotherapeutic regimen for a patient must meet **all** of the following criteria:
 - a. A known myelosuppressive regimen which includes at least two of the following agents: actinomycin, carboplatin, cisplatin, cyclophosphamide, daunorubicin, doxorubicin, etoposide, ifosfamide, topotecan
 - b. At least four consecutive cycles
 - c. Cycle length is either 14 or 21 days
 - d. Regimen **must either alternate myelosuppressive chemotherapeutic agents in an X-Y-X-Y format**, such that the same chemotherapy is given every other cycle (e.g. vincristine/doxorubicin/cyclophosphamide | ifosfamide/etoposide), **or repeat the same chemotherapeutic agents each cycle in an X-X-X-X format** (e.g. repeated cycles of cisplatin/etoposide/bleomycin). Courses eligible for this trial may occur at any time during treatment provided that they are consecutive and follow the one of the described patterns. Non-myelosuppressive anti-neoplastic treatments will not be considered for the purposes of determining eligibility. Questions regarding whether or not a patient's chemotherapy plan meets inclusion criteria will be decided by the Study Chair.
- [6] Informed consent or parental permission and assent obtained prior to trial-related activities ([Section 4.3](#))
- [7] Able and willing to comply with all study related procedures
- [8] Women of childbearing potential must agree to use adequate contraception prior to study entry and for the duration of study participation. Should a woman become pregnant or suspect she is pregnant while participating in this study, she should inform her treating physician immediately.

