 - Soy-based products: Product, dates of use. Reporting is limited to the soy-containing products described in [Section 4.8.1](#) and the patient handout in the Procedure Manual.
 - Antimicrobials: type (antibiotic, antifungal, antiviral, other); route of administration (IV, oral, other); dates of use; AE(s) precipitating use, prophylactic use, or the treatment of a presumed/known infection
 - Blood product transfusions: dates of use, blood product type (platelets, red blood cells, other), and indication ([Section 4.8.2](#))
 - G-CSF: Number of days per cycle that G-CSF was administered, primary or secondary use (planned before the cycle began or in response to prolonged neutropenia, respectively)
- Date of disease recurrence or progression, description of recurrence/progression, and site(s) of disease
- Date of secondary malignancy diagnosis, description of secondary malignancy, and site(s) of disease

- Date of death due to any cause, and description of clinical scenario surrounding the subject's death.

The procedures and assessments schedule is summarized on the Roadmaps in the Procedure Manual appendices.

Day 8 assessments must be repeated at intervening/additional weekly visits resulting from an anti-neoplastic therapy treatment delay or any other factors that causes the prolongation of a course.

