7 EVALUATION CRITERIA

7.1 Primary Endpoint

The primary endpoint of this clinical trial is the average day of neutrophil count recovery following myelosuppressive chemotherapy. Neutropenia will be defined as ANC < 500 cells/ μ l (grade 4 neutropenia per [CTCAE](#)), and the “day of recovery” for each subject during each cycle of chemotherapy will be defined as the first post-nadir day of each cycle that the ANC is \geq 500 cells/ μ l (i.e. \leq grade 3). For example, if the ANC is 400 cells/ μ l on Day 12 and 600 cells/ μ l on Day 14, then the day of recovery will be Day 14. For subjects whose ANC nadir is \geq 500 cells/ μ l, the day of recovery will be the day of the first ANC after their lowest ANC is obtained.

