8 STATISTICAL CONSIDERATIONS

8.1 Study Design

This is a multi-center, randomized, double-blind, placebo-controlled, stratified, two-arm trial with a cross-over component which results in both a between-group comparison (A vs B for Cycles 1 and 2 data) and a crossover within group difference comparison (genistein cycles minus placebo cycles data). Patterns of ANCs over time will be estimated and average day of recovery over the two cycles will be the primary comparison. Neutropenia is defined in [Section 7.1](#). For each subject, two co-primary endpoints will be estimated; a) the average day to recovery during Cycles 1 and 2, and b) the difference in the average days during genistein cycles and the average days during placebo cycles.

In addition, the study is designed to capture other clinically-relevant short-term side effects of therapy that appear to be reduced by genistein supplementation. Secondary endpoints are listed in [Section 7.2](#).

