8.2 Sample Size and Accrual

This pilot study is designed to obtain preliminary data to describe the overall pattern of ANC over time during myelosuppressive chemotherapy, assess neutropenia, and to determine whether the data support a decrease in time to recovery of 3 days for the genistein group compared to placebo. Target sample size for this pilot study was based upon results from a chart review performed at UVA which found that the mean day of recovery for pediatric cancer patients receiving myelosuppressive chemotherapy was day 16.25. Group sample sizes of 22 eligible subjects per group achieves approximately 80% power to detect a difference of 3 days with a 5% one-sided Mann-Whitney-Wilcoxon Test. These results were based on 3000 Monte Carlo samples assuming a null Poisson (mean 16.25) distribution and an alternative Poisson (mean 13.25) distribution. ANC determination and neutropenia are defined in Sections 6.3 and 7.1. Adjusting for a 10% ineligibility/drop-out rate, approximately 49 - 50 subjects may need to be accrued to the study.

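### Section 8.4 assigns no analysis to day of recovery; adjusting both co-primaries for cycle-length stratum, and the crossover one for period, is a cheap improvement

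*Combined protocol and SAP*

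**What the plan says.** - **Endpoint.** Section 7.1: the day of recovery "will be defined as the first post-nadir day of each cycle that the ANC is" at least 500 cells/µl.
- **Co-primaries.** Section 8.1 states that "average day of recovery over the two cycles will be the primary comparison", then defines (a) and (b) as co-primary and says both will be estimated. It describes the trial as stratified.
- **Sizing.** Section 8.2 reports a chart review in which "the mean day of recovery for pediatric cancer patients receiving myelosuppressive chemotherapy was day 16.25". It says that 22 eligible subjects per group "achieves approximately 80% power to detect a difference of 3 days with a 5% one-sided Mann-Whitney-Wilcoxon Test", using Poisson means of 16.25 and 13.25.
- **Randomisation.** Section 8.3: "Stratification will be based on the length of chemotherapy cycles, between 14-day" and 21-day cycles, with most patients expected in the latter.
- **Analysis.** Section 8.4 says that between-group and "crossover differences (Cycles 1 - 4) form the structure for treatment comparisons". Repeated measure models go to ANC, fever days, hospitalisation, antimicrobial use, mucositis duration and transfusions. Cochran-Mantel-Haenszel goes to categorical data. Day of recovery is in neither list.
- **Chemotherapy balance.** Criterion 5d in Section 3.1 requires the same regimen in every cycle or alternation "such that the same chemotherapy is given every other cycle".

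**The concern.** The primary objective is to estimate an effect, yet neither co-primary has a named estimator or interval. If the sizing test is carried over to (a), it ignores the randomisation stratum. The chart-review mean of Day 16.25 lies beyond the end of a 14-day cycle, while recovery is counted within each cycle, so the two strata plausibly have different recovery days. An analysis that ignores such a difference has a wider interval and a conservative test.

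For (b), Section 1.3 gives limiting period effects as a reason for the crossover, but no analysis contains a period term. Criterion 5d keeps chemotherapy the same across the two periods, so only a residual period effect, such as cumulative marrow toxicity, is at issue. The plan also does not say how the two co-primaries combine into a conclusion.

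**Working it through.** **1. The plan's own figures.** With 22 per arm, Poisson 16.25 against 13.25 and a one-sided 5% Wilcoxon test, 20,000 simulated trials give power of 0.80-0.81 (stated: about 80%). Accrual is 44/0.90 = 48.9, so 49 (stated: 49-50). Both reproduce.

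**2. Strata, co-primary (a).** Inputs: overall placebo mean 16.25 and a 3-day effect (8.2). Assumed: the 14-day stratum's mean m, its share of 4 or 7 of 22 per arm, and within-subject correlation 0.5 for the two-cycle average. If 16.25 holds for the trial's mix, the stratum gap is (16.25 − m)/(1 − share). For example, (16.25 − 14)/(1 − 4/22) = 2.75 days and (16.25 − 13)/(1 − 7/22) = 4.77 days. Section 6.3 provides for "intervening/additional weekly visits resulting from an anti-neoplastic therapy treatment delay", so cycles can lengthen and m can exceed 14.

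| m | Gap (days) | Unstratified 90% interval wider by | Power gain from stratifying, two-cycle average |
|---|---|---|---|
| 15 | 1.5-1.8 | 1-3% | under 1 point |
| 14 | 2.8-3.3 | 3-11% | about 1-4 points |
| 13 | 4.0-4.8 | 8-24% | about 3-9 points |
| 12 | 5.2-6.2 | 15-39% | up to 17 points (0.73 to 0.90, at 7 of 22) |

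The interval column spans both the single-value Poisson model of 8.2 and the two-cycle average. For m = 12-15, one-sided size is 0.016-0.047 unstratified and 0.049-0.054 with the van Elteren test. Unstratified power for the two-cycle average stays at about 0.80 or more down to m = 13.

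**3. Which variance is assumed.** Putting Poisson variance inside each stratum and adding the gap on top raises the total. At m = 13 and 7 of 22, it is 16.25 + (7/22)(15/22)(4.77²) = 16.25 + 4.9 = 21.2. Unstratified power for a single value is then 0.71. Section 8.2 assumed a total of 16.25. With the total held there, unstratified power stays at about 0.80 or more for m = 12-15, and stratifying adds 0-9 points.

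**4. Period, co-primary (b).** Let τ be the treatment effect, p an additive period effect, and nA and nB the completers. Genistein minus placebo has mean τ − p in Arm A and τ + p in Arm B.
- Bias of the pooled mean = p(nB − nA)/(nA + nB): zero at 22/22. At 18 against 22 it is p × 4/40 = 0.1, 0.2 or 0.3 day for p = 1, 2 or 3. If the plan's 10% loss (5 of 50) all fell in one arm, it is p × 5/45 = 0.11p.
- Interval inflation at 22/22 = √(1 + p²/v), where v = 2·SD²·(1 − r). Assumed (SD, r) of (3.5, 0.5), (5, 0.5) and (5, 0.3) give v = 12.25, 25 and 35. The pooled interval is 1-4%, 6-15% or 12-32% wider for p = 1, 2 or 3.
- At 18 against 22 (either arm the smaller), pooled one-sided size is 0.004-0.066, against 0.048-0.055 period-adjusted. Power at 3 days is 0.83-1.00 pooled and 0.91-1.00 adjusted.

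**5. Combining the co-primaries.** With each tested at one-sided 5%, the two statistics have correlation √((1 − r)/2). For r from 0 to 0.75, joint error is 8.0-9.2% if either suffices and 2.0-0.8% if both are required.

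**The case against.** The strongest reply is that the plan is not silent overall. Section 8.2 gives (a) a test, an alpha level, a direction and a target difference, and 8.1 defines both contrasts. The documents report no stratum means, and the chart review's cycle-length mix is not given. An unstratified test errs on the safe side. A 3-day period effect would be as large as the whole target effect. A repeated measure model could in any case carry stratum and period terms.

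Most of this stands, and it limits the size of the point. Three stronger readings that a reader might infer are not supported:
- **That the trial is underpowered without stratification.** A shortfall such as 0.71 for a single value appears only when between-stratum variance is added to the 8.2 variance.
- **That the plan carries an 8-9% false-positive risk.** That figure needs a rule under which either co-primary suffices, and the plan states no such rule. Requiring both gives about 1-2%.
- **That the plan has chosen a weaker analysis, or that (b) is biased.** Section 8.4 is silent rather than committed, and bias in (b) needs both a period effect and unequal completers.

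What remains does not depend on the assumed effects: no estimate or interval for either co-primary, no test for (b), and no use of the stratum or period for day of recovery.

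**Conclusion.** The point holds as a cheap improvement. The stated 80% power and the 49-50 accrual are correct. Naming a stratum-adjusted analysis of (a) is a gain rather than the repair of a shortfall: under 1 point of power at a 14-day mean of 15, about 1-4 points at 14 and 3-9 points at 13 for the two-cycle average, with a narrower interval throughout. Period adjustment of (b) removes the 1-32% widening at equal completers and the 0.1-0.3 day bias at 18 against 22. These sizes rest on assumed stratum means and shares, a correlation of 0.3-0.5, and a period effect of 1-3 days that is additive and common to both arms. The documents supply none of these.

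**What to change.** First reconcile the primary endpoint: the synopsis names duration of grade 4 neutropenia, while 7.1 and 8.1 use day of recovery. Then add to 8.4:

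*Subjects are analysed as randomised. (a) The Cycle 1-2 average day of recovery will be compared between arms at one-sided 5% with adjustment for cycle-length stratum (linear model with arm and stratum, or van Elteren test), reporting the estimated difference and 90% confidence interval. (b) The period difference (Cycles 1-2 average minus Cycles 3-4 average) will be compared between arms with the same stratum adjustment; the treatment effect and its 90% limits are half the arm difference, which removes any period effect.*

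The sponsor should choose one of the two methods in advance. In simulation the linear model's interval for (a) covered 0.90; the interval from inverting the van Elteren test covered 0.93-0.97, because day counts tie.

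State before unblinding how the co-primaries combine. This is the sponsor's trade-off. Testing (a) first, and (b) only if (a) succeeds, holds joint error at 5%, but at a 3-day effect cuts power for (b) from 1.00, 0.99 and 0.95 to 0.88, 0.62 and 0.61 under the three (SD, r) pairs above. Splitting alpha cuts (a) from 0.80 to 0.69.

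State also how a missing cycle is handled. Using whichever single cycle is available for (a) is unsuitable: under X-Y-X-Y it compares X alone with an X/Y average.

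**Cost:** a few sentences, no new data and no change in sample size. If strata and periods do not differ, (a) loses about 1 point (0.805 to 0.799; two-cycle average 0.89 to 0.885), and (b) loses up to 2-3 points at 18 against 22 completers (for example 0.93 to 0.91).

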Both genistein and placebo tablets will be provided by DSM Nutritional Products Europe Ltd, Switzerland.

Other study intervention(s): The chemotherapeutic regimen for each subject will be determined by the treating physician and must contain a combination of at least two agents from the following list during each of the four cycles administered in this study: actinomycin, carboplatin, cisplatin, cyclophosphamide, daunorubicin, doxorubicin, etoposide, ifosfamide, topotecan.

Criteria for evaluation (i.e. endpoints):

Efficacy: To evaluate the effectiveness of genistein administration during myelosuppressive chemotherapy, the following endpoints will be compared between genistein cycles and placebo cycles:

Primary endpoint:

- Duration of grade 4 neutropenia, defined as an absolute neutrophil count (ANC) of < 500 cells/ μ l

Secondary endpoints (per cycle):

- Severity of neutropenia
- Duration of grade 4 neutropenia during hospital admissions for febrile neutropenia
- Frequency and duration of unplanned hospital admissions due to (an) adverse event(s)
- Days with fever (temperature > 101.5° F, or > 100° F more than once in a 24-hour period)
- Incidence and severity of infections
- Duration of antimicrobial agent use
- Duration and severity of oral mucositis
- Duration and severity of peripheral motor neuropathy (in subjects receiving vincristine)
- Incidence and severity of hearing impairment and tinnitus (in subjects receiving a platinum-based chemotherapy agent)
- Number of days delayed and percent reduction of full, planned doses of anti-neoplastic agents due to (an) adverse event(s)
- Incidence of primary and secondary G-CSF use
- Number of required blood product transfusions
- Cytokine, growth factor, C-reactive protein, and homocysteine levels as well as erythrocyte sedimentation rates

Safety: Safety will be assessed by incidence and severity of AEs and changes in physical examinations.

Statistical methods:

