1.2.3 Genistein Reduces Chemotherapy-Induced Side Effects

Genistein's anti-inflammatory and antioxidant properties may counteract the oxidative damage and inflammation induced by anti-neoplastic therapy in healthy tissues, thereby reducing untoward toxicities. Adult men with localized prostate cancer who received 200 mg daily soy isoflavone supplementation (including about 96 mg genistein per day)

concomitant with their radiation therapy had reduced urinary, intestinal, and sexual adverse effects compared to subjects treated with placebo. Compliance was 100% with the study tablets and no side effects from soy supplementation were reported [28]. A small pediatric pilot study found a similar reduction in chemotherapy and radiation therapy-related toxicities with genistein supplementation [65]. In this study, eight solid tumor and brain tumor patients received the first course of therapy without soy supplementation and then received a 0.3 g tablet containing 82% soy isoflavone extract and 2.7% (8 mg) genistein daily with subsequent courses of chemotherapy. No isoflavone-related toxicities were noted and none of the children stopped taking the supplement. While these data were not statistically significant, subjects receiving genistein in conjunction with chemotherapy appeared to have less myelosuppression, less mucositis, shorter durations of antimicrobial therapy, and fewer blood product transfusions compared to cycles of chemotherapy without genistein. Furthermore, subjects who received abdominal radiation reported less pain and diarrhea while taking the genistein supplement, although this was also not statistically significant. While encouraging, these data are preliminary and additional randomized trials are needed to evaluate genistein's effect on anti-neoplastic therapy-related toxicities.

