- If ANC is < 500 cells/ μ L at any point after beginning weekly testing, resume twice weekly testing until ANC ≥ 500 cells/ μ L.
- ANC will be obtained daily during any admission for febrile neutropenia.
- All ANC values will be reported.
- Serum CRP, homocysteine, and ESR: Report raw data collected on Day 1 of Cycles 2, 3, 4, and the last day of Cycle 4
- Cytokine Panel and Isoflavone Panels: Draw and process specimen per the Procedure Manual on Day 1 of Cycles 1, 2, 3, 4, and the last day of Cycle 4
- Weight and height on Day 1 of each cycle
- The following **target AEs** must be assessed and the maximum grade reported for each cycle in addition to standard AE/SAE reporting ([Section 9](#)):
 - Neutropenia
 - Febrile neutropenia, with maximum associated temperature per cycle
 - Fever, including number of days per cycle, for temperatures $> 101.5^{\circ}$ F, or $> 100^{\circ}$ F more than once in a 24-hour period (report maximum temperature)
 - Infections and Infestations: Maximum grade for any AE listed in this CTCAE category. Infections meeting the AE reporting threshold must be listed individually.
 - Oral mucositis
 - Tinnitus (subjects receiving platinum-based chemotherapy only)
 - Hearing impairment (subjects receiving platinum-based chemotherapy only)
 - Peripheral motor neuropathy (subjects receiving vincristine only)
- Report per cycle:
 - Study supplement:
 - Total number of tablets taken

- Subject compliance with study medication dosing as determined by self-reported administration reports and supplement reconciliation
- Reason for dose change, if applicable. Any AE(s) precipitating a dose reduction must be reported even the minimum AE reporting threshold is not otherwise met ([Section 9.2](#)).
- Anti-neoplastic treatment delay(s):
 - Total number of days delayed from planned schedule
 - Cause for delay: AE, or reason other than AE
- Anti-neoplastic agent dose reduction(s):
 - Delayed agent(s)
 - Planned dose(s)
 - Actual dose(s)
 - Cause for dose change: AE, or reason other than AE
- All unplanned or prolonged hospitalizations due to (an) AE(s) ([Section 9.1.9](#)):
 - Date of admission or start of prolongation and discharge date
 - Causes/diagnoses precipitating hospitalization or prolonged hospitalization
- Concomitant medication review at each scheduled visit for the following:

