7.2 Secondary Endpoints (per cycle)

“Incidence” refers to both the frequency of an event per subject and the number of affected subjects in this study.

- **Severity of neutropenia**
- Duration of **grade 4 neutropenia during hospital admissions for febrile neutropenia**
- Frequency and duration of unplanned or prolonged **hospitalizations** due to (an) AE(s) ([Section 9.1.9](#))
- Days with **fever** (temperature > 101.5° F, or > 100° F more than once in a 24-hour period)
- Incidence and severity of **infections**
- Duration of **antimicrobial use**
- Duration and severity of oral **mucositis**
- Duration and severity of **peripheral motor neuropathy** (in subjects treated with vincristine)
- Incidence and severity of **hearing impairment** and **tinnitus** (in subjects treated with a platinum-based chemotherapy agent)
- Number of days of **delays and percent reduction of full planned doses of anti-neoplastic agents due to (an) AE(s)**
- Incidence of primary and secondary **G-CSF use**
- Number and cause of required **blood product transfusions**
- **Serum cytokine levels:**
 - G-CSF, granulocyte-macrophage colony stimulating factor (GM-CSF), interferon- α (IFN- α), IFN- γ , IL-1 β , IL-1 receptor antagonist (IL-1RA), IL-2 receptor (IL-2R), IL-4, IL-5, IL-6, IL-7, IL-8, IL-10, IL-12, IL-13, IL-15, IL-17, TNF- α .

- **Chemokines:** eotaxin, IFN- γ induced protein 10 (IP-10), monocyte chemotactic protein 1 (MCP-1), monokine induced by IFN- γ (MIG), macrophage inflammatory protein 1- α (MIP-1 α), MIP-1 β , Regulated upon Activation Normal T cell Expressed and presumably Secreted (RANTES).
- **Serum growth factor levels:** epidermal growth factor (EGF), fibroblast growth factor-basic (FGF-basic), hepatocyte growth factor (HGF), vascular endothelial growth factor (VEGF)
- **Serum CRP levels, homocysteine levels, and ESRs**

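### Section 8.4 analyses antimicrobial duration only in subjects admitted with febrile neutropenia, a post-randomisation subset that the per-cycle endpoint does not mention and whose unit is undefined

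*Combined protocol and SAP*

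**What the plan says.** The Synopsis lists "Duration of antimicrobial agent use" among the per-cycle secondary endpoints, and Section 7.2 lists the same outcome per cycle. Neither limits it to FN admissions. Where an FN limit was wanted, it was written into the endpoint itself. That happens once in the list, for the duration of "grade 4 neutropenia during hospital admissions for febrile neutropenia".

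Section 8.4 says that repeated-measures models "will be used to assess differences in raw ANC, daily ANC, days with fever, duration of hospitalization", and the sentence ends with "duration of antimicrobial use for subjects admitted with febrile neutropenia". The Synopsis paragraph on statistical methods repeats it. In the same section, transfusions are to be "documented and compared during genistein and placebo cycles using repeated measure models", with no FN limit, and mucositis duration is handled in the same unrestricted way.

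FN is an on-treatment event. Section 6.3 lists it as a target adverse event to be assessed each cycle: "Febrile neutropenia, with maximum associated temperature per cycle".

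**The concern.** However the sentence in Section 8.4 is parsed, antimicrobial duration is analysed only in subjects admitted with FN. That group forms after randomisation, through an event of the kind that genistein is hypothesised to reduce (Section 1.1). A subject or cycle spared an FN admission can drop out of the analysis instead of counting as zero days.

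The endpoint is part of the trial's rationale. Section 1.2.3 cites, from a small pediatric pilot, "shorter durations of antimicrobial therapy, and fewer blood product transfusions compared to cycles of chemotherapy without genistein". If genistein works partly by preventing admissions, the restricted analysis answers a different question from the one the endpoint poses.

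Two further points are unspecified. The text says subjects, but not over which cycles an admission counts, although Section 8.4 plans both a Cycles 1-2 between-group comparison and a four-cycle crossover comparison. It is also unclear whether the FN phrase reaches back to fever days and hospital days.

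**Working it through.** The plan gives no figure on this point. Its power statement (about 80% with 22 per group) concerns the primary comparison and does not enter here. The check is a reading of the text followed by an illustration.

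**Scope of the phrase.** The list in Section 8.4 opens with raw ANC, which is measured in everyone, and the section begins with the complete ANC pattern over all four cycles. The FN phrase therefore cannot sensibly cover the whole list. Daily ANC, on the other hand, is required only for FN admissions (Section 6.3: "ANC will be obtained daily during any admission for febrile neutropenia"). So the list does not settle whether fever days and hospital days are restricted. If hospital days are, that conflicts with the hospitalisation endpoint, which covers any unplanned admission due to an adverse event.

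**Illustration: inputs, all assumed, since the documents give no FN rates or course lengths.** Placebo admission rate per cycle p = 20%, 40% or 60%; genistein rate q. FN antimicrobial courses last 3 days (half) or 8 days (half), so mean D = 5.5. Cycles are independent, and there are no antimicrobial days outside FN admissions.

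**Formulas** for mean days per cycle at admission rate r:
- All subjects: r × D
- Subjects admitted in Cycles 1-2: r × D / (1 - (1 - r)²)
- Admitted cycles only: D
- Ever admitted, all four cycles contributing: r × D / (1 - (1 - p)²(1 - q)²). Both treatments share this denominator, given two cycles on each and no period or carryover effect.

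**At p = 40%:**
- Pattern 1, admissions halved at random (q = 20%). All subjects: 1.1 - 2.2 = -1.10. Cycles 1-2: 1.1/0.36 - 2.2/0.64 = 3.056 - 3.4375 = -0.38. Admitted cycles: 5.5 - 5.5 = 0. Ever admitted: -1.10/0.7696 = -1.43.
- Pattern 2, only 3-day courses prevented (q = 20%, D = 8 on genistein). All subjects: 1.6 - 2.2 = -0.60. Cycles 1-2: 1.6/0.36 - 3.4375 = 4.444 - 3.4375 = +1.01. Admitted cycles: 8 - 5.5 = +2.5. Ever admitted: -0.60/0.7696 = -0.78.
- Pattern 3, same admission rate, courses one day shorter (D = 4.5). All subjects: 1.8 - 2.2 = -0.40. Cycles 1-2: -0.40/0.64 = -0.625. Admitted cycles: -1.0. Ever admitted: -0.40/(1 - 0.6⁴) = -0.40/0.8704 = -0.46.

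Genistein minus placebo, days per cycle, at p = 20 / 40 / 60%:

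| Pattern | All subjects | Admitted in Cycles 1-2 | Admitted cycles | Ever admitted |
|---|---|---|---|---|
| 1 | -0.55 / -1.10 / -1.65 | -0.16 / -0.38 / -0.69 | 0 | -1.14 / -1.43 / -1.79 |
| 2 | -0.30 / -0.60 / -0.90 | +1.15 / +1.01 / +0.78 | +2.5 | -0.62 / -0.78 / -0.98 |
| 3 | -0.20 / -0.40 / -0.60 | -0.56 / -0.625 / -0.71 | -1.0 | -0.34 / -0.46 / -0.62 |

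In pattern 1 the Cycles 1-2 selection keeps 29% to 42% of the all-subject difference (0.16/0.55 to 0.69/1.65). At 40% against 20%, 0.64 × 22 = 14.1 placebo and 0.36 × 22 = 7.9 genistein subjects would enter.

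**Robustness.** Letting admission risk vary between subjects (beta, mean 0.4, precision 2), pattern 2 still reverses among subjects admitted in Cycles 1-2 (4.71 against 3.93 days), and the four-cycle crossover difference keeps its sign (-0.94). A separate latent-severity simulation, in which the milder episodes are prevented and course length has no direct effect of treatment, gave +0.8 to +1.4 days among admitted subjects against -0.6 to -1.1 over all subjects. Placebo/genistein admission rates there were 30/20, 40/30, 50/30 and 60/40%. At 40/40% both differences were 0.

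**The case against.** The strongest reply is that the attenuation and reversal depend on readings the text does not state. Section 8.4 says neither subjects admitted in Cycles 1-2 nor admitted cycles. An equally literal reading is subjects ever admitted on study, each contributing all their cycles. The two treatments then share a denominator, so the sign is kept. So is the relative effect when all antimicrobial days fall within FN admissions (-50% in pattern 1, -27% in pattern 2). Reversal also needs genistein to prevent mainly short courses, which nothing in the documents suggests. Length of treatment once admitted is a fair descriptive question in a pilot that aims to estimate, given the standard care described in Section 1.2.1.

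Much of this stands. A reader might infer that the plan biases the antimicrobial result, or will reverse it. The documents do not support that, because they name no unit and give no FN rates or course lengths. A reader might also infer that prevented admissions vanish from the trial. They do not: admission frequency and infection incidence remain separate endpoints. Nor can one say that fever days and hospital days are restricted, only that the wording leaves it open.

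What the reply does not remove is the mismatch. Even on the ever-admitted reading, the absolute difference is per cycle in a selected group. In patterns 1 and 2 it is 1/0.9216 = 1.09 to 1/0.4816 = 2.08 times the all-subject value. The readings also disagree in size and sometimes in sign, so the unit has to be fixed in advance.

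**Conclusion.** The point holds as a mismatch between endpoint and analysis, with an undefined unit. The only planned analysis of antimicrobial duration is confined to a post-randomisation subset, and the endpoint is not. If admission is counted within Cycles 1-2 or by cycle, the comparison is no longer randomised. Under the stated assumptions it can be attenuated (to between 29% and 42% of the all-subject difference, or to 0), reversed, or enlarged when genistein only shortens courses. If ever-admitted subjects contribute all four cycles, the sign is kept and the absolute difference is scaled up. All these sizes rest on assumed admission rates and course lengths and, except in the robustness runs, on independent cycles.

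For fever days and hospital days the finding is ambiguity only. This is a secondary endpoint in a pilot, and the primary comparison and sample size are unaffected. The change should be made, because it is cheap and settles what will be estimated.

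**What to change.** In Section 8.4 and the Synopsis:

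- Analyse antimicrobial duration, fever days and hospital days per cycle in all treated subjects over all observed cycles, within the repeated-measures framework already planned.
- Score 0 only where the cycle was observed and no event occurred. Treat cycles after discontinuation without data as missing. Subjects who stop the supplement move to follow-up (Section 4.9). Target adverse events are then not routinely collected (Section 9.2.3.1), and Table 3 shows no concomitant-medication review.
- Report treatment and prophylactic antimicrobial days separately, using the reason for use already recorded (Sections 4.8.2 and 6.3).
- Keep the FN qualifier only for daily ANC and for grade 4 neutropenia during FN admissions. Label these and any other FN-subset analysis as descriptive, and name the unit: subject or cycle, and over which cycles admission is counted.

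For observed cycles no new data are needed: Section 6.3 already collects fever days per cycle, admission and discharge dates, and antimicrobial dates. The cost is a wording amendment with IRB approval (Section 11.2) and a zero-heavy outcome that needs a suitable model, such as a count model. Days outside FN admissions also enter the endpoint and dilute relative effects. At 40% in pattern 1, one such day in every cycle moves -50% to -34% (2.1 against 3.2), and two move it to -26% (3.1 against 4.2). The absolute difference does not change. Separating prophylaxis limits this dilution.
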